9.3 POWER CALCULATION

Using baseline from the peer-reviewed study that examined the effect of a DNA-based diet on obese individuals (Arkadianos et al. 2007), at 90% power with an alpha of 0.05, 50 participants are required in each group to

demonstrate a between-group difference in effect size of -0.5 mmol/L as the primary outcome. This assumes a SD of the baseline to endpoint difference of 0.6 mmol/L. The sample size will be increased by 20% to 60 participants per arm of the study in order to compensate for participants lost to follow up (this includes the 10% risk that a given participant will have of becoming type 2 diabetic within a 12 month period due to their prediabetic state, and a subsequent addition to account for those participants who may be lost to follow up for other reasons).

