For each of the primary and secondary outcomes, formal statistical analysis will be based on appropriate linear models. From each linear model, an estimate of the magnitude of the treatment effect i.e. the difference in mean outcomes between the control arm and intervention arm, will be derived, together with adjusted (least squares) means, 95% confidence intervals, and associated p-values. Initial exploratory analyses of these models will include relevant baseline covariates, including baseline values of the endpoint, and

all covariates that are statistically significant will be retained in the model for the purposes of deriving the final treatment effect outcomes. Baseline values of the endpoint will be retained in each model regardless of statistical significance.

All analyses will be conducted using two-sided tests and at a significance level of 5%.

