### **1.14 Planned analysis**

The primary analysis will be conducted under the ITT principle using modified ANCOVA as described above. Raw and adjusted mean differences in PFG at week 6 between the intervention and control arm will be presented with 95% confidence interval (95% CI). The adjusted mean difference will be estimated using a linear regression model of week 6 FPG to baseline PFG and treatment arm adjusted for age and sex.

The primary null hypothesis is of no difference in week 6 FPG adjusted means between the intervention and the control arms. It will be tested against the alternative hypothesis of a difference between the two groups.

$$H_0: \mu_0 = \mu_1$$

$$H_A: \mu_0 \neq \mu_1$$

Where  $\mu_0$  and  $\mu_1$  are the week adjusted trimmed mean FPG in respectively the control and intervention group. The null hypothesis will be rejected if the robust adjusted 95% CI of the mean difference does not include 0.

- Power of the analysis

With 60 participants in each group and assuming that the average PFG changes from baseline to the week 6 will be -0.6 mmol/l in the intervention arm and -0.1 mmol/l in the control arm, that the baseline standard deviation (sd) of PFG is 0.7, the post-intervention sd is 0.6, and that the correlation between baseline and post-intervention measurement range between 0.6 and 0.4, the analysis will have a power greater than 0.9 to detect a difference between both arms.

- Sub-group and additional analysis of the primary outcome

An interaction between baseline FPG and treatment effect will be tested.

No sub-group analysis is planned for the primary endpoint.

- Sensitivity analysis

The robustness of the results will be tested using a non-parametric model as described above.

Both results will be presented and discrepancies will be discussed.

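### The inputs in protocol 9.3 need 32 participants per group, not 50, and neither document shows where 50 comes from

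*Protocol*

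**What the plan says.** Protocol 9.3 points to baseline data from a published study of a DNA-based diet in obese people. It states that "at 90% power with an alpha of 0.05, 50 participants are required in each group to" detect the target effect. The stated aim is to "demonstrate a between-group difference in effect size of -0.5 mmol/L as the primary outcome". On variability it gives one figure: "This assumes a SD of the baseline to endpoint difference of 0.6 mmol/L". It then adds an allowance for loss to follow-up: "The sample size will be increased by 20% to 60 participants per arm of the study". It names no statistical test and does not say whether alpha is one- or two-sided.

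Protocol 9.4 supplies the sidedness: "All analyses will be conducted using two-sided tests and at a significance level of 5"%. The primary comparison is intervention against control (SAP, Study design), and SAP 1.20 makes no multiplicity adjustment.

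SAP 1.14 has a separate power statement for 60 per arm. It takes mean changes of -0.6 and -0.1 mmol/L, so again a difference of 0.5. Its variability assumption is "that the baseline standard deviation (sd) of PFG is 0.7, the post-intervention sd is 0.6". How closely the two readings are taken to agree is given next: "that the correlation between baseline and post-intervention measurement range between 0.6 and 0.4". Its conclusion is that "the analysis will have a power greater than 0.9 to detect a difference between both arms". It does not derive 50.

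**The concern.** The standardised difference in 9.3 is 0.5/0.6 = 0.83, which is large. Fifty per group is well above what 90% power normally needs for an effect of that size. Section 9.3 builds its 60 per arm directly on the 50, so the protocol's sample-size justification rests on a number that its own inputs may not produce.

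If they do not, either the 50 or one of the inputs is misstated. The candidates have different consequences. If only the 50 is too high, the trial has more power than it claims. If the SD actually used was well above 0.6, the margin is smaller than the printed figures suggest.

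**Working it through.** All calculations are on the raw mmol/L scale, with two equal groups.

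**Inputs.** Difference d = 0.5, SD of change s = 0.6, power 90%, alpha 0.05 (protocol 9.3); two-sided (protocol 9.4).

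**Step 1. Try to reproduce 50.** Normal approximation:

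n per group = 2 (z for 0.975 + z for 0.90)² s²/d² = 2 (1.960 + 1.2816)² x 0.36/0.25 = 30.26, so 31.

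Two-sample t-test (noncentral t): 31.25, so 32. The stated 50 is not reproduced. It exceeds 32 by 18 per group (18/32 = 56%).

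**Step 2. Power on the stated inputs (t-test).**

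| n per group | Power for 0.5 mmol/L, SD 0.6 |
|---|---|
| 31 | 89.8% |
| 32 | 90.7% |
| 50 | 98.5% |
| 60 | 99.5% |

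At 50 per group, 90% power is reached for a difference of about 0.39 mmol/L.

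**Step 3. Try the other SDs in the documents.** From SAP 1.14, with correlation r between baseline and week 6:

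- SD of change = sqrt(0.7² + 0.6² - 2r x 0.7 x 0.6) = sqrt(0.85 - 0.84r)
- SD after baseline adjustment = 0.6 x sqrt(1 - r²)

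| r | SD of change | n for 90% | Power at 50 | Power at 60 | Adjusted SD | n for 90% |
|---|---|---|---|---|---|---|
| 0.4 | 0.717 | 45 | 93.2% | 96.6% | 0.550 | 27 |
| 0.5 | 0.656 | 38 | 96.5% | 98.5% | 0.520 | 24 |
| 0.6 | 0.588 | 31 | 98.8% | 99.6% | 0.480 | 21 |

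With baseline adjustment, power is at least 99.4% at 50 and above 99.8% at 60. The baseline SD of 0.7 used alone gives 42.2, so 43. None of these is 50. The table also confirms the SAP's claim of power above 0.9 at 60 per arm.

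**Step 4. Try other design features** (d = 0.5, SD 0.6, two-sided, 90% power unless stated).

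- Bonferroni for two or three comparisons: 36 to 41.
- Three-arm ANOVA, over several patterns of means: 29 to 38.
- Rank test at relative efficiency 0.955 or 0.864: 33 or 37.
- 95% power: 38 to 39.
- Loss to follow-up: already excluded, since 50 x 1.20 = 60 applies it after the 50.

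**Step 5. What would give 50.** These are illustrations; neither document states any of them.

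- Two-sided 5%, 90% power, d = 0.5: an SD of about 0.76.
- One-sided 5% with SD 0.6 x sqrt(2) = 0.849: 49.3 by the normal approximation, so 50 per group (51 by t-test).
- One-sided 5% with SD 0.6: 24.66 by the normal approximation, so 25 per group, which is 50 in total for two arms (26 per group by t-test). At 25 per group the two-sided power is 82.3%.

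**The case against.** Four points can be made for the plan.

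*The source is named but not visible.* Section 9.3 refers to a cited study, and SAP 1.13 refers to an annex on that study's glucose data that is not in the supplied text. This stands as a limit on the finding: the origin of 50 cannot be determined here. It does not rescue the statement, because 0.6 is the only SD that 9.3 prints and it does not lead to 50.

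*A two-sided route exists using SAP figures.* With SD 0.7 at both time points and r = 0.4, the SD of change is sqrt(2 x 0.49 x 0.6) = 0.767. The normal approximation then gives 49.4, so 50 (t-test 50.4, so 51). Unlike the one-sided illustrations, this respects protocol 9.4. However, it contradicts the SAP's post-intervention SD of 0.6 and the change SD of 0.6 in 9.3. It shows that the SD could be the misprinted item, which is a reason to ask the sponsor, not a reproduction of 50.

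*The planned analysis is ANCOVA, later a robust regression, not a t-test.* This is true, but adjustment for baseline lowers the requirement. A loss from robust estimation would need relative efficiency of about 31.25/50 = 0.63 to reach 50, and no document claims that.

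*The error is harmless in a self-described pilot.* On the printed figures this is right: 60 per arm is adequate and no analysis changes. It is not assured for every possible origin. If the SD really was 0.849, an unadjusted two-sided test would have about 83% power at 50 and 89% at 60.

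**Conclusion.** The concern holds. On its stated inputs, with two-sided testing as in 9.4, protocol 9.3 needs 32 per group by t-test (31 by normal approximation), against 50 stated. The 50 gives 98.5% power, not the 90% claimed.

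This rests on equal groups, an unadjusted comparison of change scores and the raw scale. Baseline adjustment on the SAP's inputs requires fewer participants, so it widens the gap. Which element of 9.3 is wrong cannot be settled from the documents.

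The consequence is limited. The discrepancy is in the conservative direction and confined to 9.3, and SAP 1.14 supports 60 per arm independently. It should be corrected because a sample-size statement ought to follow from its own inputs, but it does not threaten the trial.

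**What to change.** Restate protocol 9.3 so that n, SD, sidedness, power and test agree.

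- **If the printed inputs stand:** say that 32 per group are required for 90% power (two-sample t-test, two-sided 5%, SD of change 0.6 mmol/L), that 60 per arm are randomised, and that 50 evaluable per arm give about 98% power for 0.5 mmol/L. If a full 20% of the 60 were lost, 48 would remain, with 98.1% power.
- **If other inputs were used:** state the SD, its source and the test that gave 50, consistent with the two-sided 5% rule in 9.4.

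The sponsor should check the calculation record before choosing between these. The cost is one or two sentences in 9.3, with no change to enrolment, design, primary test or SAP.

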9.4 ANALYSIS OF PRIMARY AND SECONDARY OUTCOME MEASURES

Data will be analysed after all primary and secondary outcomes have been recorded for the last participant. The primary analysis will be conducted under the ITT principle using modified analysis of covariance (ANCOVA) (Yang & Tsiatis 2001). Raw and adjusted mean differences in PFG at week 6 between the intervention and control arm will be presented with 95% confidence interval (95%CI). The adjusted mean difference will be estimated using a linear regression model of week 6 FPG to baseline PFG and treatment arm adjusted for age and sex. An interaction of baseline FPG with the indicator for treatment arm will be included. PFG will be log transformed and variables will be centred.

The primary null hypothesis is no difference in W6 FPG between the intervention and the control arm. It will be rejected if the adjusted 95%CI of the mean difference does not include 0. The robustness of the results will be tested using PP analysis and two alternative models (repeated measure mixed model and non parametric model). Missing data will be imputed using the multiple imputation with chain equation (MICE) method if there is no evidence against the assumption of data missing at random.

The secondary analysis will be conducted under the ITT principle. The ANCOVA will be used to compare mean difference in FPG, weight, BMI, mass, waist, fasting lipids and blood pressure at the different time points (W6, W12 and W26). In addition, mixed models will be used to compare the overall changes in these outcomes over the all follow up period. Adequacy of the models will be assessed through residual plots and Shapiro-Wilk tests for normality. Non-parametric methods may be used in case of severe departure from normality. In the addition, logistic regression model will be used to compare the proportion of participants with IGR between the two arms. Change in dietary habits will be analysed using polytomous regression.

For each of the primary and secondary outcomes, formal statistical analysis will be based on appropriate linear models. From each linear model, an estimate of the magnitude of the treatment effect i.e. the difference in mean outcomes between the control arm and intervention arm, will be derived, together with adjusted (least squares) means, 95% confidence intervals, and associated p-values. Initial exploratory analyses of these models will include relevant baseline covariates, including baseline values of the endpoint, and

all covariates that are statistically significant will be retained in the model for the purposes of deriving the final treatment effect outcomes. Baseline values of the endpoint will be retained in each model regardless of statistical significance.

All analyses will be conducted using two-sided tests and at a significance level of 5%.

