## 1.9 Analyses of quantitative data

Continuous outcomes will be compared between groups using the modified analysis of covariance (ANCOVA). This approach has been chosen because it is more powerful than other alternatives such as t-test.

A linear regression model will be used to analyse the association between post-intervention values of the outcomes with intervention arm adjusting for their baseline value, participant age and sex.

Let  $y_{it}$  denote the outcome value for individual  $i$  at time  $t$ ,  $x_i$  her covariates (e.g. sex, age) and  $d_i$  her intervention arm. The ANCOVA model is given by:

$$y_{it} = \beta_0 + \beta_1 y_{i0} + \beta_2 x_i + \gamma d_i + \varepsilon_{it}$$

An extension of the basic ANCOVA model will consider an interaction between the intervention indicator and the baseline values to test the assumption that the treatment effect varies with baseline status.

In addition, changes in continuous outcomes from baseline will be analysed using a linear regression model of the difference between the outcome value at visit and its baseline value. Using the same notation, the change model is

$$\Delta y_{it} = y_{it} - y_{i0} = \beta_0 + \beta_1 x_i + \gamma d_i + \varepsilon_{it}$$

Covariates will be centered in the analyses. Robust linear regression *lmrob* from the R package *robustbase* will be used for the ANCOVA analysis unless specified otherwise. It uses the MM-estimator to estimate the regression coefficient accounting for departure from normality of the outcomes.

Assessment of models' goodness of fit will include careful examination of residuals using graphical methods (scatter plot, boxplot and QQ plot) and detection of outliers. In addition, equality of the post-treatment variances will be tested using Levene's test.

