## Analysis of the primary endpoint

### 1.13 Derivation

*Measurement.* Under the protocol, participants are scheduled to have an OGTT at week 6 (visit 6, D42+/- 3 days). Plasma glucose at 0 minute will be measured after 12 hours fasting and before the 75g glucose load via an OGTT.

*Data transformation.* Available data from Arkadianos et al. suggests that PFG may not be normally distributed (see Annex). In the study by Arkadianos, post intervention PFG showed significant departure from normality with significant skewness (0.8, Agostinos test; p = 0.04). By contrast, no significant departure from normality was observed for PFG changes from baseline (Annex). Although the log transformation has been suggested in the literature, this transformation applied to Arkadianos data did not improve the normality of PFG distribution. Using the box-cox method, the best transformation was achieved with the boundary value of -2.

For this analysis, the preferred approach to handle departures from normality and outliers will be to use of robust statistical methods.

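### Protocol 9.4 and SAP 1.9, 1.13 and 1.14 specify different primary tests of week-6 FPG, and no supplied sentence says which one governs

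*Protocol*

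**What the plan says.** **Protocol 9.4** describes the primary analysis as modified ANCOVA, estimated by linear regression of week-6 FPG on baseline FPG and arm, adjusted for age and sex. It then says: "An interaction of baseline FPG with the indicator for treatment arm will be included. PFG will be log transformed and variables will be centred". A later paragraph, which expressly covers the primary outcome, derives the treatment effect from linear models "together with adjusted (least squares) means, 95% confidence intervals, and associated p-values", and adds that "all covariates that are statistically significant will be retained in the model for the purposes of deriving the final treatment effect outcomes".

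**SAP 1.9** writes the ANCOVA on the outcome itself, with baseline value, age and sex as covariates and no interaction. The interaction appears as an extension. The fit is by lmrob unless specified otherwise: "It uses the MM-estimator to estimate the regression coefficient accounting for departure from normality of the outcomes".

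**SAP 1.13** reports that the log transformation, applied to data from the earlier DNA-diet study, "did not improve the normality of PFG distribution", and that "the preferred approach to handle departures from normality and outliers will be to use of robust statistical methods".

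**SAP 1.14** rejects the null hypothesis on the robust adjusted 95% CI and lists the baseline interaction as an additional analysis. The two quantities in its null hypothesis "are the week adjusted trimmed mean FPG in respectively the control and intervention group".

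Both power statements are in mmol/L. Protocol 9.3 sizes the trial to "demonstrate a between-group difference in effect size of -0.5 mmol/L as the primary outcome", and SAP 1.14 uses changes of -0.6 and -0.1 mmol/L.

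**The concern.** Both documents reject when an adjusted 95% CI excludes 0, but they apply that rule to different intervals. The protocol's interval is for a difference in mean log FPG, that is, a ratio once back-transformed, and no back-transformation is stated. The SAP's is for a location difference in mmol/L. The protocol's primary model also depends on the data through its covariate rule, even if that rule only adds to age and sex. The SAP's model is fixed.

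The trial is open label (SAP, Study design) and endpoint assessment is not blind (SAP 1.4). If the primary test is not unique, one could be picked after results by arm are known, and a borderline result could be declared either way.

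**Working it through.** **1. The texts side by side**

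| Element | Protocol 9.4 | SAP 1.9, 1.13, 1.14 |
|---|---|---|
| Scale | log FPG | no transformation stated; log reported as unhelpful |
| Estimator | linear regression, least squares means | lmrob (MM) |
| Baseline-by-arm term | in the primary model | extension or additional analysis |
| Covariates | baseline, age, sex, plus a significance-based rule | baseline, age, sex |
| Parameter | difference in mean log FPG | trimmed means in H0, MM coefficient in the fit |

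The SAP is also inconsistent with itself. An MM regression coefficient is not a difference in trimmed means, and no trimming proportion is given. SAP 1.21 lists WRS2 as well as robustbase, so the software list does not settle what was meant.

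**2. Which document governs**

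The SAP Background says that it details the planned analyses. SAP 1.7 cites protocol version 0.18 of 16/07/2018. Protocol 12.2 mentions early 2020, so the supplied protocol text is later than the version the SAP cites, and it still carries the log.

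**3. The plan's own power figures**

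- SAP 1.14 claims power above 0.9 with 60 per arm. ANCOVA SD = 0.6 × √(1 − r²), which is 0.550 at r = 0.4 and 0.480 at r = 0.6. For a difference of 0.5 this gives power of 99.87% and 99.99%. With change scores, SD = √(0.49 + 0.36 − 2r × 0.42) = 0.717 to 0.588, and power is 96.9% to 99.7%. The claim is reproduced on the mmol/L scale.
- Protocol 9.3 states 50 per group. Its inputs (0.5, SD 0.6, 90% power, two-sided 0.05) give 2 × (1.960 + 1.282)² × 0.36/0.25 = 30.3, so 31. The 50 is not reproduced, but it errs towards more participants and does not bear on this point.
- On the log scale, -0.5 mmol/L is a ratio that depends on the control mean, which the documents do not give. For assumed means of 5.5 to 6.5 mmol/L it is 5.0/5.5 = 0.909 to 6.0/6.5 = 0.923.

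**4. How often the decision changes (simulation)**

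- Inputs from SAP 1.14: SDs 0.7 and 0.6, r = 0.4-0.6, control change -0.1. Skewness of 0.8 is the SAP 1.13 figure; normal data were also used.
- Assumed: mean FPG 6.0 mmol/L, a uniform treatment shift, and the smaller effects of -0.2 and -0.3.
- Size: 50 or 60 per arm, ten settings, 7,154-8,505 trials each, Monte Carlo SE at most 0.5 points.
- lmrob was not available, so bisquare MM regression from another R package stood in for it.

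Percentage of trials in which the two 5% decisions differ:

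| True difference (mmol/L) | Protocol model v SAP MM | Log + interaction v raw least squares | Raw least squares v MM |
|---|---|---|---|
| -0.5 | 0.01-0.5 | not split | not split |
| -0.3 | 4.5-8.9 | 1.4-3.4 | 4.2-10.6 |
| -0.2 | 8.2-14.7 | 2.8-3.9 | 7.7-16.3 |

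The interaction alone accounts for at most 0.8%. A separate simulation (60 per arm, r = 0.5, error skewness 0, 0.8 and 1.5, 1,500 trials per setting) gave 0-0.1% at -0.5, 4.1-7.1% at -0.3 and 8.5-16.2% at -0.2.

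With no true effect, the protocol model rejects in 4.5-5.6% of trials and MM in 4.5-5.3%. Taking whichever is significant rejects in 5.9-7.9%.

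If trimmed means are meant literally (assumed 20% trimming, Yuen test on baseline-adjusted values), the decision differs from MM in 4.1-6.7% at -0.3 and 6.0-8.5% at -0.2.

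**The case against.** The best defence is that there is no real ambiguity. SAP 1.13 considers the log, says why it was dropped, and states a preferred approach; SAP 1.9 names the function and SAP 1.14 gives one rejection rule. On that view Protocol 9.4 holds a stale sentence. Some pages of both documents were not available, and SAP 1.7 cites the older protocol only for data collection. This stands in part: the SAP does read as a deliberate refinement, and a statement of precedence may sit on a missing page. But none is in the supplied text, and the later protocol text keeps the log.

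The estimator contrast is also less explicit than the log and the interaction. SAP 1.14 itself speaks of a linear regression model, and the protocol's least squares wording describes adjusted means. This stands. The contrast with most numerical effect therefore has the weaker textual basis, and the explicit conflicts alone change 1.4-3.9% of decisions at the smaller effects.

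SAP 1.14 promises a non-parametric check with discrepancies discussed, and the protocol adds per-protocol and mixed-model checks. These help, but none compares log least squares with MM regression on the original scale.

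A reader might infer that the two documents could reach opposite conclusions about the treatment. That is not supported. In further simulations at r = 0.5, with 50 or 60 per arm, the two estimates had the same sign whenever decisions differed, and the median larger p-value was about 0.06-0.08. These are borderline crossings of 0.05.

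**Conclusion.** The conflict is in the text and concerns the primary test, so it should be fixed: scale, interaction, covariate rule and, less explicitly, estimator differ, and the SAP's null hypothesis does not match its own estimator. The practical effect is negligible at the planned -0.5 mmol/L (at most about 0.5% of simulated trials). At assumed effects of -0.2 to -0.3, roughly 5-15% of trials cross the 0.05 boundary. Choosing after the fact takes type I error to about 6-8%.

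These rates rest on the assumed mean FPG and smaller effects and on a stand-in for lmrob; multiple imputation was not modelled. The textual conflict depends on none of this. A reader might also infer that one of the tests is invalid or that the trial is underpowered. Neither follows: each test alone holds close to 5%, and simulated power at -0.5 is at least 99.0% for log least squares, raw least squares and MM. For the covariate rule, the claim is only that the primary model becomes data-dependent. The rule names no candidate covariates, so its effect on error rates cannot be sized.

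**What to change.** - **Protocol 9.4:** delete the log transformation, keeping the centring. Move the baseline-by-arm term to an additional analysis, as in SAP 1.14. Exempt the primary outcome from the significance-based covariate rule.
- **Both documents:** state one primary model, namely week-6 FPG in mmol/L on arm with centred baseline FPG, age and sex, fitted by lmrob as SAP 1.9 already specifies. Ordinary least squares may be added as a sensitivity analysis.
- **SAP 1.14:** replace the trimmed mean in H0 with the robust adjusted difference. If trimmed means were intended, name the method and the trimming proportion instead.
- **Precedence and timing:** state that the SAP governs the primary analysis, update the protocol version cited in SAP 1.7, and fix and date the choice before outcome data by arm are seen.

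The cost is small: wording changes plus one optional model, with no change to data collection or sample size. In simulation at -0.3 mmol/L (50 per arm, r = 0.5), MM loses about 2 points of power against raw least squares with normal errors (78.2% v 80.1%) and gains about 4 with skewed errors (84.5-84.9% v 80.3-80.8%).

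### Protocol 9.4 gives two conflicting covariate rules for the primary estimate, one fixed in advance and one driven by significance; under the second, the 5% test can become slightly too liberal

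*Protocol*

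**What the plan says.** Protocol 9.4 describes the primary adjusted mean difference twice.

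- **Fixed rule.** The estimate comes from a "linear regression model of week 6 FPG to baseline PFG and treatment arm adjusted for age and sex". An interaction between baseline glucose and arm is to be included.
- **Selection rule.** Further down, the section states: "For each of the primary and secondary outcomes, formal statistical analysis will be based on appropriate linear models". Candidate covariates, described only as relevant, are first tried out in an exploratory step, after which "all covariates that are statistically significant will be retained in the model for the purposes of deriving the final treatment effect outcomes". The one exemption is: "Baseline values of the endpoint will be retained in each model regardless of statistical significance".

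The SAP follows the fixed rule. Section 1.14 has the primary difference "estimated using a linear regression model of week 6 FPG to baseline PFG and treatment arm adjusted for age and sex". Section 1.9 models continuous outcomes by "adjusting for their baseline value, participant age and sex", and the opening of the Secondary endpoints section carries those analyses over to the continuous secondary variables. The SAP contains no covariate selection step. It treats the baseline-by-arm interaction as an extension (1.9) and as an additional test (1.14).

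Protocol 9.2 and Table 2 stratify randomisation by gender and by age (40 or under, over 40). Both documents set the significance level at 5%, and the Protocol adds that tests are two-sided.

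**The concern.** The selection rule names the primary outcome and says that it produces the final treatment effect, so it cannot be read as a side analysis. It conflicts with the fixed rule in three ways:

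- Age and sex are in the model under the fixed rule. Under the selection rule they stay only if significant, although they define the randomisation strata.
- The candidate list is open. The Protocol says only that covariates should be relevant, and it does not describe the screening procedure.
- The primary null hypothesis is rejected when the adjusted 95% interval excludes 0. In a borderline case the covariate set can therefore decide the result. The trial is open label, and the SAP (1.4) says that endpoint assessment is not blind to arm.

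Two analysts working from Protocol 9.4 alone could report different primary estimates, intervals and p-values. In addition, the refitted model's standard error treats the retained covariates as if they had been chosen in advance, so the actual error rate may differ from 5%.

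**Working it through.** **Inputs from the documents.** Two-sided 5% level (Protocol 9.4); 60 per arm (Protocol 9.2); baseline SD 0.7, post-intervention SD 0.6 and correlation 0.4 to 0.6, with 0.5 used (SAP 1.14).

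**Assumptions, not in the documents.**
- The number of candidates: 2 to 20, including age and sex. As a guide to the upper end, the SAP 1.8 baseline table lists 22 variables besides randomisation group, or 21 without baseline fasting glucose.
- In the main runs, the candidates other than age and sex are mutually correlated at 0.3. Two of them have a true coefficient of 0.2 residual SD. Age and sex are balanced between arms and not prognostic.

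**Data model under no treatment effect.** Week 6 value = slope × baseline + covariate terms + error, where
- slope = 0.5 × 0.6 / 0.7 = 0.43
- residual SD = 0.6 × √(1 − 0.5²) = 0.52

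**Analyses compared, all by least squares.**
- (a) Fixed: arm, baseline, age, sex.
- (b) Fit all candidates with arm and baseline, keep those with p < 0.05, refit with arm and baseline.
- (c) As (b), but with the arm left out of the screening fit.

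**The plan's figure first.** Analysis (a) should reject in 5% of null trials, and it does. The Monte Carlo standard error with 90,000 trials is √(0.05 × 0.95 / 90,000) = 0.07 percentage points.

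| Candidates (60 per arm, 90,000 trials) | (a) fixed | (b) arm in screen | (c) arm not in screen | (b) − (a) |
|---|---|---|---|---|
| 5 | 5.07% | 5.61% | 5.21% | 0.54 |
| 10 | 5.04% | 5.56% | 5.01% | 0.52 |
| 20 | 4.93% | 5.94% | 4.99% | 1.01 |

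**Sensitivity to the assumptions.**
- Runs of 30,000 trials at 60 per arm, with age and sex either not prognostic or prognostic, gave for (b) 5.6% and 5.5% (5 candidates), 5.8% and 5.7% (10), and 6.3% and 6.1% (20).
- A separate simulation of 20,000 trials at 60 per arm gave for (b) 5.8%, 5.7% and 6.4%, and for (c) 4.9% to 5.2%.
- Over every setting tried with 5 to 20 candidates, at 50 and 60 per arm, (b) ran from about 5.1% to 6.9%, mostly 5.3% to 6.3%. Screening without the arm gave 4.7% to 5.4% over all settings.
- With two candidates, (b) gave 4.9% to 5.3% in the 10,000-trial runs and 5.4% in the separate simulation.

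**What was not simulated.** The Protocol's log transformation and baseline-by-arm interaction, and the SAP's robust MM-estimator.

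**The case against.** The strongest reply is that the SAP has already settled the matter. Its Background says that it details the planned analyses, it fixes the covariates for the primary and continuous secondary endpoints, and it selects nothing. An analyst who follows the SAP will not meet the problem. This is a good reason to rate the effect as modest, but it does not remove the conflict, because neither document states precedence. SAP 1.7 cites Protocol version 0.18 of 16/07/2018. The Protocol under review refers in 12.2 to the COVID-19 outbreak of early 2020, so its text is later and still carries the retention rule.

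A second reply is that the inflation depends on steps the Protocol leaves unstated. This stands. A reader might infer that the primary test is anti-conservative in any event, and the documents do not support that. They give no candidate list. The only adjustment covariates they name besides the baseline value are age and sex, and with two candidates the error rate is close to 5%. They also do not say whether the arm is in the screening model, and without it there is no meaningful inflation. Screening with the arm included is the natural reading, since the models being explored are those that yield the treatment effect, but it remains a reading.

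A third reply is that this is a pilot with no multiplicity adjustment, so a shift of half a point to one point matters little. That bears on priority. It does not excuse two rules for one primary estimate.

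**Conclusion.** The point holds: Protocol 9.4 is wrong as written. It gives two incompatible covariate rules for the primary estimate, and the selection rule also conflicts with the SAP. This rests on the text alone and needs no simulation.

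The effect on the error rate is modest and conditional. With the arm in the screening model, an assumed 5 to 20 candidates and 60 per arm, type I error is roughly 5.5% to 6.4% under least squares. The largest runs put the excess over the fixed model at about 0.5 to 1 percentage point. Values near 6.9% appeared only at the edge of the settings tried and should not be quoted as typical. Nor should a reader infer that the SAP's planned analysis is inflated: it has no selection step, and the fixed-covariate model held 5% in the least-squares runs.

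**What to change.** 1. Delete the retention rule from Protocol 9.4, including the exploratory step that feeds it.
2. State that every primary and continuous secondary comparison uses the pre-specified baseline value, age and sex, as in SAP 1.9 and 1.14, whether or not these are significant.
3. Put any other covariate in a sensitivity analysis labelled as such, with the covariates named in advance.
4. Reconcile the baseline-by-arm interaction: Protocol 9.4 includes it in the primary model, while SAP 1.14 only tests it separately. Without this step, removing the retention rule would still leave the two primary models different.
5. Say which document governs if they differ.

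The cost is a wording change. Sample size, randomisation, visits and data collection are unaffected, and the SAP already uses the fixed covariate set.
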